#### LIST OF ABBREVIATIONS AND RELEVANT DEFINITIONS

ABR ABR form, General Assessment and Registration form, is the

application form that is required for submission to the accredited Ethics Committee (In Dutch, ABR = Algemene Beoordeling en

Registratie)

AE Adverse Event
AR Adverse Reaction

CCMO Central Committee on Research Involving Human Subjects; in

**Dutch: Centrale Commissie Mensgebonden Onderzoek** 

DSMB Data Safety Monitoring Board

EEG Electroencephalography

EU European Union

**EudraCT** European drug regulatory affairs Clinical Trials

FNAR False negative alarm rate
GCP Good Clinical Practice

IB Investigator's Brochure

IC Informed Consent

Kempenhaeghe Academic Centre of Epileptology Kempenhaeghe

METC Medical research ethics committee (MREC); in Dutch: medisch

ethische toetsing commissie (METC)

QoL Quality of Life

(S)AE (Serious) Adverse Event SDD Seizure Detection Device

Sponsor The sponsor is the party that commissions the organisation or

performance of the research, for example a pharmaceutical

company, academic hospital, scientific organisation or investigator.

A party that provides funding for a study but does not commission it

is not regarded as the sponsor, but referred to as a subsidising

party.

SEIN Stichting Epilepsie Instellingen Nederland

SUSAR Suspected Unexpected Serious Adverse Reaction

UMCU University Medical Center Utrecht

Wbp Personal Data Protection Act (in Dutch: Wet Bescherming

Persoonsgevens)

WMO Medical Research Involving Human Subjects Act (in Dutch: Wet

#### Medisch-wetenschappelijk Onderzoek met Mensen)

#### **SUMMARY**

**Rationale:** Various remote and wearable sensor devices have become available for the detection of potentially dangerous seizures, with limited impact on epilepsy care so far. Both our remote and our wearable seizure detection devices (SDDs) have been extensively tested and proven highly sensitive. Yet the home performance in children, an important target population, had been insufficiently studied.

# Objective:

1. To test the performance of the wearable SDD (NightWatch) prospectively and the remote SDD (automated video and audio analysis) retrospectively in children in a family home setting. 2. To assess the feasibility, cost-effectiveness and cost-utility of NightWatch in children.

**Study design:** A multicenter home-based medical device intervention study with prospective validation of our wearable SDD.

**Study population:** 60 children (ages 4-16 years) with refractory epilepsy (≥1 major nocturnal seizure per week) recruited from the outpatient clinics of one of the participating epilepsy centers (Stichting Epilepsie instellingen Nederland (SEIN), Academic Centre of Epileptology Kempenhaeghe (Kempenhaeghe), University Medical Center Utrecht (UMCU)).

**Intervention (if applicable)**: Phase I: Two months of baseline (usual care); Phase 2: Two months of nocturnal seizure monitoring at home, using NightWatch and the remote SDD.

Main study parameters/endpoints: The diagnostic performance of NightWatch and the remote SDD algorithms, i.e. sensitivity, positive predictive value, false alarm rate and % time with uninterrupted signal output. We will evaluate feasibility of NightWatch through surveys on quality of life, sleep, parental strain, interviews with parents/guardians and neurologists, and a value sensitive design group session. We will also perform a cost-effectiveness and cost-utility analysis by medical consumption and costs questionnaires.

Nature and extent of the burden and risks associated with participation, benefit and group relatedness: Implementing SDDs will not pose any direct or substantial risk. Study participation can be a burden though, due to impact of the devices on privacy, number of false alarms and time spent on the questionnaires and interviews. Application of the SDDs, however, might offer better insight into the actual number of nocturnal seizures in a child, change in medical management and facilitate appropriate interventions in major motor seizures. If reliable, SDDs may improve the night rest of both patient and parents/guardians.

#### 1. INTRODUCTION AND RATIONALE

Epilepsy impacts ~180.000 people in the Netherlands [1]. Despite advances in treatment, one third of all people with epilepsy continue to have seizures [2] that adversely affect quality of life (QoL) [3,4]. Poor seizure control is the major determinant of impaired QoL. Seizures impact not only individuals with epilepsy but also their guardians [5-7] as seizures are (1) unpredictable, (2) may cause loss of control and (3) cause life threatening situations, including injuries, status epilepticus and sudden unexpected death in epilepsy [8]. Convulsive seizures carry the greatest mortality risk, particularly those occurring at night, as these are often unwitnessed [9]. Childhood epilepsy has also a severe impact on parental QoL [10] and monitoring devices can help to improve parental anxiety levels, quality of sleep, and QoL [11]. Various non-EEG based signals have been assessed for the detection of potentially dangerous seizures [12]. Seizure detection devices (SDDs) have had, however, limited impact on epilepsy care so far. Barriers to SDD implementation include lack of external validation and high rate of false alarms. Most SDDs rely on a single modality. This approach likely explains limited sensitivity and specificity [12]. Previous studies validated multimodal algorithms for wearable sensors (accelerometry & heart rate) and demonstrated the feasibility of remote sensors (audio & video) to detect seizures [13-17]. Preliminary results indicate that the performance of the NightWatch is superior to a commonly used bed sensor, the Emfit. Our multicenter prospective trial in a residential population of adults with epilepsy and learning disabilities (LICSENSE trial, NTR4115) shows a median sensitivity per person of 85.7% with a positive predictive value of 49.3% and a median false negative alarm rate of 0.04 per person per night [18]. The interim analysis of our recent trial in 21 children (LICSENSE phase III) indicated that the algorithms needed an adjustment as in children higher heart rates are more common and less specific features for epilepsy appear thus increasing the number of false alarms. In response we updated our algorithm (with less emphasis on heart rate changes and more weight on movement changes). This approach still reach 80% sensitivity and 50% PPV in the majority (80%) of subjects (adults and children). This current prospective home-based trial is needed as a final validation step for the new algorithm in children and to evaluate feasibility of NightWatch. Former trials were performed without actual alarms. The current trial also enables us to get insight in the real life situation of children and their parents/guardians by focusing on feasibility. The literature has so far only discussed these needs with questionnaires but without insight into the home situation [19].

Remote SDDs may provide an alternative for wearable sensors, especially when they are not tolerated. We recently demonstrated the feasibility of video algorithms to detect convulsive seizures in a small clinical cohort (a learning set of 50 subjects with 72 convulsive seizures and a test set of 12 individuals and 50 seizures). Performance analysis resulted in 100%

sensitivity of detecting tonic-clonic seizures and 57% of detecting non-vital minor seizures. 67% of latencies were ≤ 10 seconds and the median false detection rate was 0.78 per night [13]. A previous study found a sensitivity of audio detection of 81% by analyzing seizure specific sounds in 10 subjects with 112 major seizures [15]. All false positive alarms (mean value: 1.29 per night) were due to minor seizures and 4 seizures (3%) were missed because of lack of sound and 10 (9%) because of sounds below the system's threshold. The company CLB Acoustic Monitoring has developed several acoustic monitoring devices for use in health care. They collected a large database of distinct sounds, including seizure related ones. For both remote SDD components (video and audio) long-term databases are needed to determine false alarm rates.

The current study will test (1) the performance of NightWatch with a fixed algorithm and (2) optimize the algorithms for the remote SDD (video and audio).

All studies on any SDD have been performed in a clinical (hospital/institution) setting. These study populations do not represent the general epilepsy population, and (sleep) settings in the hospital clearly differ from at home. Our study will test the SDDs in a family home setting and will be the first real field SDD implementation study. By focusing on the patient and family perspective, we will obtain crucial feedback on which performance is feasible for them and in which way parents/guardians experience support from an SDD. This study design will comply with the concepts of the Dutch Health Board's recommendations for novel devices [20].

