#### 2. OBJECTIVES

# **Primary Objective:**

Diagnostic performance of our wearable multimodal SDD (NightWatch) to detect major nocturnal motor seizures in children at home. Diagnostic performance of NightWatch will be measured prospectively by means of sensitivity, positive predictive value, false alarm rate and % time with uninterrupted signal output.

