#### 4. STUDY POPULATION

#### 4.1 Population (base)

Around 20,000 children carry the diagnosis of epilepsy in the Netherlands [23]. Most children with severe or difficult to treat epilepsy are under specialized epilepsy care in SEIN, Kempenhaeghe or UMCU. This study will include 60 children with refractory epilepsy (≥1 major nocturnal seizure per week) from one of the above epilepsy care facilities. There will be no restrictions on seizure etiology.

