#### 4.3 Exclusion criteria

A potential subject who meets any of the following criteria will be excluded from participation in this study:

- Intensive non-epileptic movement patterns such as severe choreatiform movements, intensive sleep walking, or frequent night terrors (> 1/week).
- Minor motor seizures only, i.e. non-generalized or short (< 10 sec.) tonic seizures or isolated myoclonias that are self-limited and do not require intervention.
- Presence of a pacemaker or cardiac arrhythmias that may generate false alarms (e.g. supraventricular tachycardia).
- Inability to comply to the trial procedure.
- Skin characteristics (e.g. dark skin color or tattoo) that may affect photoplethysmography and thereby influence performance of the NightWatch.
- Dependence on another SDD (e.g. Emfit or saturation monitor). Simultaneous use of a baby phone (or other types of microphones) is permitted.
- Subjects who are not sleeping alone in the bed (i.e. co-sleeping in the
  parents'/guardians' bed influences the remote SDD). We do not allow subjects and
  parents/guardians to change their sleeping habits for the duration of the study only.

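### Children whose data prompted the current NightWatch algorithm are not kept out of its validation cohort or its primary performance estimates

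*Combined protocol and SAP*

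**What the plan says.** Section 1 (Introduction and Rationale) gives the history of the algorithm. "The interim analysis of our recent trial in 21 children (LICSENSE phase III) indicated that the algorithms needed an adjustment", because higher heart rates in children were producing more false alarms. It continues: "In response we updated our algorithm (with less emphasis on heart rate changes and more weight on movement changes"). The result of the change is summarised as "This approach still reach 80% sensitivity and 50% PPV in the majority (80%) of subjects (adults and children"), without naming the data set. The role of the present trial follows: "This current prospective home-based trial is needed as a final validation step for the new algorithm in children".

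Two further statements define the test. Section 1 says "The current study will test (1) the performance of NightWatch with a fixed algorithm", and the primary objective in section 2 says "Diagnostic performance of NightWatch will be measured prospectively by means of sensitivity, positive predictive value, false alarm rate", along with signal availability.

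On recruitment, 4.1 notes that "Most children with severe or difficult to treat epilepsy are under specialized epilepsy care in SEIN, Kempenhaeghe or UMCU", and these are the three recruiting centres. Section 4.2 sets conditions on age, diagnosis and seizure frequency, treating centre and consent. Section 4.3 opens with "A potential subject who meets any of the following criteria will be excluded from participation in this study" and lists seven criteria, none of which concerns earlier participation in a LICSENSE trial. The nearest is reliance on a different detection device, which is another matter. Section 11.2 (recruitment) adds no such screen. Section 10.1 describes performance with descriptive statistics only and gives no flag or separate estimate for earlier participants.

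**The concern.** A validation study shows how a device performs in people who had no part in shaping it. By the protocol's account, the current version of NightWatch was shaped in response to results in 21 children. A site that follows 4.2 and 4.3 as written could enrol one of them, and 10.1 would count that child like any other.

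The plan gives some reason to think that a child's earlier data carry information about that child's later performance. Sections 3 and 11.4 offer individual tailoring based on a child's own recordings, followed by a second monitoring period in the same child. If that expectation is sound, children who informed the update may do somewhat better under it than new children would.

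The update responded to false alarms, so PPV and false alarm rate may be at least as exposed as sensitivity. All three are primary measures. The Introduction itself names missing external validation as a barrier to the use of such devices, so the independence of this cohort is a large part of what the trial offers.

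**Working it through.** **Inputs from the documents.** 21 children in the earlier trial (section 1); 60 children planned, about 540 seizures, targets of 80% sensitivity and 50% PPV, and 384 observations for a 5% interval at 95% confidence (4.4).

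**Inputs that are assumptions.** The number *k* of the 21 who re-enrol, and the gap *g* by which their sensitivity exceeds that of new children. The documents give neither. I take *k* from 0 to 21 and *g* from 2 to 10 points.

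**Step 1: the plan's own figures.**
- n = z² p(1 − p)/d² with z = 1.96, p = 0.5 and d = 0.05 gives 384.1, matching 384. With p = 0.8 it gives 245.9, so the stated figure is the one for p = 0.5, with 5 points as a half-width.
- 60 children × 1 seizure per week × 9 weeks = 540.
- Half-width with 540 seizures: 1.96 × √(0.8 × 0.2/540) = 3.4 points at 80%, and 1.96 × √(0.5 × 0.5/540) = 4.2 points at 50%.

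These figures reproduce and are not in dispute. They treat seizures as independent, as 4.4 does.

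**Step 2: largest possible overlap for this cohort.** 21/60 = 35% of children. The smallest is zero.

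**Step 3: shift in overall sensitivity.** With equal weight per child, shift = (k/60) × g.

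| k re-enrolled | g = 2 points | g = 10 points |
|---|---|---|
| 0 | 0 | 0 |
| 3 | 0.1 | 0.5 |
| 6 | 0.2 | 1.0 |
| 12 | 0.4 | 2.0 |
| 21 | 0.7 | 3.5 |

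If new children had a sensitivity of 80%, the bottom row would read as 80.7% to 83.5%. Only its upper end reaches the planned half-width of 3.4 points; with a few re-enrolled children the shift is well inside it. If seizures are pooled instead, the weight is the re-enrolled children's share of seizures rather than k/60.

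**Step 4: precision after the fix.** If these children are excluded and others recruited, there are still 60 children and about 540 seizures, so precision does not change. If they are enrolled but left out of the primary estimates without replacement:
- k = 3: 57 × 9 = 513 seizures; half-width 3.5 points at 80% and 4.3 at 50%.
- k = 21: 39 × 9 = 351 seizures; half-width 4.2 points at 80% and 5.2 at 50%.

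**The case against.** The strongest reply is that nothing in the primary analysis reuses development data. The measurements are prospective and the NightWatch algorithm is fixed, so a returning child contributes only new nights. The setting also changes: section 1 places all earlier detection-device studies in a hospital or institution, whereas this trial is in the family home. A reader might infer that the primary result is partly calculated on the recordings used for tuning. The documents do not support that. The possible overlap is of children, and any optimism is probably smaller than if recordings were reused.

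It is also fair to say that the update is described as a general reweighting, for a reason that applies to children at large. That the recordings of the 21 served as the tuning set is a reasonable inference from the wording, but it is not stated. Performance after the update is quoted for adults and children together, so other subjects were assessed too.

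Nor is any overlap shown. The documents do not say where the 21 were recruited. To re-enter, a child would have to meet the current age and seizure-frequency criteria, pass every exclusion and consent again.

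Finally, a reader might infer that returning families would distort the T0 answers on expectations and demand, or would be especially easy to recruit. The first sits badly with section 1, which says that former trials ran without actual alarms; the second has no source in the documents.

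All of this limits the size of the problem. It does not close the gap: no criterion bars such a child, and no analysis sets the child apart.

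**Conclusion.** The point holds as a possibility that the plan leaves open, not as a demonstrated bias. As written, children whose results prompted the current algorithm may enter the cohort meant to validate it and count fully in the primary estimates. The effect on sensitivity lies between zero and 3.5 points for gaps of up to 10 points. It is half a point or less with three such children, and reaches the upper end only if all 21 return and the largest assumed gap applies. These figures rest on unsourced gaps and equal weight per child. PPV and false alarm rate could move in the favourable direction too, but the documents give no basis for sizing that.

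The change is still worth making. A larger sample would not remove such a bias if the share of returning children stayed the same, and the safeguard costs little.

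**What to change.** Either of two changes would do.

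1. Add an exclusion to 4.3 for children whose recordings were used to develop or adjust the current NightWatch algorithm, and have it checked at screening against the group's own trial lists.
2. Record earlier participation with the T0 baseline information. In 10.1, base the primary performance estimates on children not used in development, and report the all-children estimates alongside. This also deals with any such child who is already enrolled.

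Under either option, state which trials and recordings supplied the tuning data, since the rule cannot be applied without that.

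The first option shrinks the eligible pool slightly. Of the 21 children in the earlier trial, at most 21 are lost, but the exact number depends on which trials supplied tuning data. The second option keeps every child in the study, including for feasibility and costs, but loses some precision in the primary estimates: in the extreme case the half-width at 80% goes from 3.4 to 4.2 points. If the check finds no overlap, nothing is lost and the report can state that the validation cohort is independent.

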# Secondary Objectives:

- Diagnostic performance of our remote SDD (video and audio) to detect major nocturnal motor seizures in children at home. Diagnostic performance will be measured retrospectively by means of sensitivity, positive predictive value and false alarm rate and % time with uninterrupted signal output.
- Feasibility of NightWatch with a mixed methods approach focusing on Acceptability, Demand, Implementation, Practicality, Expansion and Limited-efficacy testing (caregiver strain (CSI), sleep (PSQI), QoL (EQ-5D-5L)) and impact of the SDD on parents/guardians and children (interview).
- Economic evaluation from a societal prospective of NightWatch involving a combination of a cost-effectiveness analysis (CEA) and a cost-utility analysis (CUA). (See 8.1.2. Methods)

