#### 3. STUDY DESIGN

This is a home-based medical device intervention study, with prospective validation of our wearable device, including 60 children with refractory epilepsy (≥1 major nocturnal seizure per week) from three epilepsy centers (SEIN, Kempenhaeghe, UMCU). Subjects will receive usual care during the first two months (non-exposure period), followed by home-based nocturnal monitoring for two months (exposure period) [See Figure 1]. In both periods parents/guardians will be invited to keep a seizure diary. The NightWatch wirelessly transmits sensor outputs to a monitor in the parents/guardians room to alert them in case of a suspected seizure [See Figure 2]. Simultaneous video and audio recordings will be stored and analyzed offline.[21] Both algorithms will generate marks in dataflow, but these marks will not be used to alert the parents/guardians and will only be examined by the researchers.[See figure 3] The video material will also be used to screen for false negative alarms and to improve the algorithm when necessary (comparable with the LICSENSE study design, NTR4115).

Trial nurses will check the validity of the generated alarms and marks in a blinded way and screen 5% of the nocturnal video recordings without alarms. The LICSENSE trial demonstrated a median false negative alarm rate (FNAR) of 0,03 per subject per night with 10% screening of all nights. We believe that 5% screening will also be feasible, but we will perform an interim analysis after inclusion of 20 subjects to see whether FANR is still reasonably low (below 0,1 per night). If this is not the case, we will increase screening to 10% of all nights. The LICSENSE trial found a high Cohen's kappa (0.77) for inter-observer agreement between trial nurses and neurologists. Therefore, this expert review of the nocturnal video recordings by the trial nurses will serve as the gold standard. Cases of doubt will be discussed with a neurologist. Seizures will be stratified according to type (tonic-clonic, >30 seconds tonic, hyper motor and major) and severity (minor/major).

Parents/guardians will be invited to articulate their user experiences at focus meetings. Video tracings of detected seizures of their child will be shown to the parents/guardians who will be asked to indicate whether they would want to be alerted for these events or not. Results from these meetings will be included in the discussion on which type of seizures should be alarmed by SDDs.

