# 8.1.2 Secondary study parameters/endpoints (if applicable)

- 1. Validation of remote SDDs (video and audio):
  - Sensitivity;
  - Positive predictive value;
  - False alarm rate;
  - % Time with valid signal allowing proper detection.
- 2. The feasibility of the NightWatch focusing on Acceptability, Demand, Implementation, Practicality, Expansion and Limited-efficacy testing [22].

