#### **10 STATISTICAL ANALYSIS**

#### 10.1 Primary study parameter(s)

Performance of the algorithms (sensitivity, positive predictive value, false alarm rate and % time with valid signal allowing proper detection) will be expressed using descriptive statistics.

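### The plan does not say which version of the remote video and audio algorithms is reported as validated, or that scoring comes before optimisation

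*Combined protocol and SAP*

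**What the plan says.** The Introduction gives the two systems different tasks. The study will test "the performance of NightWatch with a fixed algorithm and (2) optimize the algorithms for the remote SDD (video and audio".

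The remote system's accuracy is nevertheless a study result:

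- The Summary puts it among the main parameters: "The diagnostic performance of NightWatch and the remote SDD algorithms".
- Section 2 makes it a secondary objective: "Diagnostic performance will be measured retrospectively by means of sensitivity, positive predictive value and false alarm rate".
- Section 8.1.2 titles the endpoint "Validation of remote SDDs (video and audio".

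On data and procedure, section 3 says "Simultaneous video and audio recordings will be stored and analyzed offline", then "Both algorithms will generate marks in dataflow", and "Trial nurses will check the validity of the generated alarms and marks in a blinded way". The same section allows the video to be used, where needed, to improve an algorithm that it does not name. Section 11.6 allows coded study data to go to the audio supplier for optimisation of its algorithms, and gives no timing.

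The only analysis statement on algorithm performance is in section 10.1: the measures "will be expressed using descriptive statistics".

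**The concern.** Validation means scoring an algorithm on data that played no part in choosing its settings. If thresholds or weights are adjusted to a set of recordings and the adjusted version is scored on those recordings, the estimates describe development performance. Sensitivity and PPV are then expected to be too high and the false alarm rate too low. Descriptive reporting does not help, because the bias is in the point estimate.

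What is at stake is whether a reader of the results could tell which kind of estimate the remote figures are. The false alarm rate matters most here, since the Introduction says that long-term data are needed to determine it for both remote components.

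**Working it through.** This is mainly a question of reading the sections against each other.

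**1. Is the remote version fixed?** The Introduction calls NightWatch fixed and gives optimisation as the task for the remote algorithms. The contrast means that the remote version may change during the study.

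**2. Can study recordings feed that change?** For audio, yes: section 11.6 says so directly. For video, the support is indirect. It rests on the optimisation aim in the Introduction and on the section 3 sentence about improving an unnamed algorithm. Under section 8.3 the hard drives are exchanged every two weeks, so recordings become available while the study is still running.

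**3. Are the reported estimates tied to one version?** Section 3 implies that some version is run, because it produces marks and nurses check them. No section names that version, locks it, or says that the reported sensitivity, PPV and false alarm rate come from those marks.

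**4. Is there an order, split or resampling rule?** Section 10.1 has none. Section 10.2 covers feasibility and section 10.3 the economic evaluation. Safeguards do appear elsewhere. The earlier video work had a learning set of 50 subjects and a test set of 12. An individually adjusted NightWatch algorithm is re-tested prospectively in a second two-month period (sections 3 and 11.4). Neither safeguard covers the remote algorithms in this study.

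**5. Size.** The Introduction gives one set of performance figures for each remote algorithm and no comparison of learning with test performance, so the optimism cannot be derived. The following illustration shows how far it depends on assumptions.

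- Section 4.4 expects about 540 seizures, which reproduces as 60 children × 9 weeks × 1 per week.
- Suppose that the best of k candidate settings is chosen on those seizures, and that every setting has a true sensitivity of 80%.
- Expected optimism = √(0.80 × 0.20 / 540) × √DE × √(1 − ρ) × E(k). DE is the design effect, ρ the correlation between settings, and E(k) the expected maximum of k independent standard normal values.
- The first factor is 1.72 percentage points.
- With k = 5, ρ = 0.8 and DE = 1: 1.72 × 0.447 × 1.16 = 0.9 points.
- With k = 20, ρ = 0 and DE = 1: 1.72 × 1.87 = 3.2 points.
- With an assumed intraclass correlation of 0.1 and 9 seizures per child, DE = 1 + 8 × 0.1 = 1.8. Multiplying by √1.8 = 1.34 gives 1.2 and 4.3 points.

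The values of k, ρ and the intraclass correlation are all assumptions. Retraining a flexible model could give more, and a scored-first version would give none. This is not an estimate for the trial.

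**The case against.** The strongest reply is that the plan probably does score first. Marks are generated and adjudicated under blinding, which implies an existing version, and video is used for improvement only when needed. The Introduction also names other material that could support development, namely the earlier video learning set and the audio supplier's sound database. The remote work is openly retrospective and described as optimisation, and the word validation is attached to it only in the section 8.1.2 heading. The result is secondary in sections 2 and 8.1.2, it is descriptive, and section 3 says that remote marks alert nobody.

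Much of this stands. A reader might infer from the Introduction and section 8.1.2 that the remote algorithms will certainly be tuned and validated on the same recordings. The documents do not say that, and section 3 points towards an existing version being run.

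It does not close the gap. Blinded review protects the reference standard; it does not stop tuning and testing on the same data. The check of audio fragments before release in section 11.6 concerns identifying content such as speech, and is not a rule that scoring is complete. A probable order of work is not a specified one.

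A reader might also infer that the primary result is at risk because section 3 does not name the algorithm to be improved. The Introduction fixes the NightWatch algorithm, and individual adjustment belongs to a separate second period. The documents therefore do not support that inference.

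**Conclusion.** The concern holds as a gap in specification. The plan assigns optimisation to the remote algorithms, allows study data to be used for it, and reports their accuracy as validation, without naming a version or an order. Development performance could therefore be published as validation without any departure from the protocol.

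The direction of the possible bias is clear: sensitivity and PPV up, false alarm rate down. It arises only if a tuned version is scored on its tuning recordings, which the plan permits but does not state. The size is not derivable from the documents.

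The effect is confined to a secondary, descriptive result, although the Summary lists it among the main parameters. The primary NightWatch result is untouched. Severity is minor to moderate.

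**What to change.** Amend sections 8.1.2 and 10.1 and the data-sharing text in section 11.6:

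1. Lock and version-number the video and audio algorithms that generate the marks before any study recording is scored.
2. State that the performance of those locked versions in all children is the validation result.
3. Use study recordings for remote optimisation, or release them to the audio supplier for that purpose, only after that scoring is complete.
4. Label any optimised version as development (apparent) performance. Optionally, estimate it by cross-validation at child level, with all tuning repeated inside the folds.

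The cost is protocol wording and a later data release to the audio supplier. The nurses already review the marks of the version that is run, so steps 1 to 3 add no review work and remove no child from the validation estimate. The label in step 4 costs nothing. Cross-validation would cost more, because tuning is repeated in each fold and new marks need blinded review; for that reason it is left optional.
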